5. TREATMENT PLAN

We will conduct a prospective Phase II trial of nivolumab in 134 treatment naïve patients with ccRCC. Eligible patients with biopsiable (biopsied) disease will receive nivolumab 240 mg IV every 2 weeks x 6 doses (2 cycles) then nivolumab every 3 weeks at a dose of 360 mg IV for 4 doses (2 cycles) followed by nivolumab 480 mg IV every 4 weeks. Tumor response will be assessed at weeks 12, 18 and 24 and then every 12 weeks. For patients who experience RECIST 1.1 defined PD, but remain clinically stable (and asymptomatic), a confirmatory scan after 4-6 weeks of additional therapy is suggested. Patients with persistent PD at confirmatory scan will be evaluated for enrollment on Part B of this study. Symptomatic patients may be evaluated for Part B immediately. Patients without confirmed PD can continue on nivolumab therapy.

Patients who experience symptomatic or confirmed PD (or have best response of SD at 48 weeks/end of Cycle 6) on nivolumab monotherapy will be eligible for consideration for Part B. Part B involves the addition of ipilimumab for up to 4 doses while maintaining nivolumab therapy. Dose of ipilimumab will be 1 mg/kg every 3 weeks together with nivolumab changed to 3 mg/kg every 3 weeks for up to 4 doses (must complete by week 16 of Part B). Nivolumab will revert to 360 mg every 3 weeks after the completion of treatment with ipilimumab for 4 doses (2 cycles) followed by nivolumab 480 mg IV every 4 weeks (must be started between week 13-19). Patients will be followed with serial imaging assessments weeks 12, 18 and 24 and then every 12 weeks after the initiation of ipilimumab. The tumor measurements at the time of (or within 4 weeks of) ipilimumab institution will be the new baseline.

Patients for Part B must still meet the eligibility criteria for initial study enrollment. Patients with Grade 3 toxicity on nivolumab monotherapy, serious symptomatic disease that in the opinion of the site investigator requires immediate use of an alternative treatment approach or continued PR/CR will be excluded from enrolling in Part B. It is estimated that roughly half of the patients accrued to the first-line treatment will go on to enroll in Part B.

An additional biopsy will be performed of a metastatic lesion at time of confirmed PD in all patients enrolling in Part B. Confirmation of tumor in the biopsy specimen must occur prior to initiation of treatment on Part B. Subjects unable to undergo a new tumor biopsy and have tissue slow frozen for scRNASeq are not eligible for Part B.

An additional cohort of 40 non-ccRCC patients will be enrolled and analyzed separately for evidence of anti-tumor activity (CR, PR and SD and PFS at 1 year of nivolumab). These patients will also be eligible for participation in Part B (as described for patients with ccRCC). We anticipate that the accrual of these 40 patients will be able to be completed within the 1.5 years needed for accrual of the ccRCC patients.

5.1 Part A: Nivolumab Administration

Nivolumab will be given every 2 weeks x 6 doses (2 cycles) at a dose of 240 mg Intravenously (IV) then every 3 weeks at a dose of 360 mg IV for 4 doses (2 cycles) followed by nivolumab 480 mg IV every 4 weeks until toxicity, disease progression, SD at 48 weeks (end of Cycle 6) or complete response with a maximum of 96 total weeks (12 weeks induction, 84 weeks maintenance) Patients with disease progression (at any time) or SD at 48 weeks (end of Cycle 6) will be eligible to be considered for participation in Part B of the study.

Part A

Drug	Dose	Route ³	Schedule ¹	Cycle Length	Cycles/Weeks
Nivolumab	240 mg	IV over 30 minutes	Day 1, 15, and 29	6 weeks	C1 and C2 Weeks 1-12
Nivolumab	360 mg	IV over 30 minutes	Day 1 and 22	6 weeks	C3 and C4 Weeks 13-24
Nivolumab	480 mg	IV over 30 minutes	Day 1, 29 and 57	12 weeks	C5-C10 Weeks 25-96
¹ A window of \pm 3 days may be applied to all study visits to accommodate observed holidays, inclement weather, scheduling conflicts etc. Date and time of each drug administration should be clearly documented in subject's chart and electronic case report forms (eCRFs).					
² Treatment will continue until toxicity, PD, SD at 48 weeks (end of Cycle 6) or CR with a maximum of 96 weeks					
³ . Infusion window of \pm 10 minutes					

5.2 Part B: Nivolumab + Ipilimumab

Patients with Grade 3 toxicity on nivolumab monotherapy, (excluding endocrine toxicity), serious symptomatic disease that in the opinion of the site investigator requires immediate use of an alternative treatment approach or continued PR/CR will be excluded from enrolling in Part B. It is estimated that roughly half of the patients accrued to the first line treatment will go on to enroll in Part B. Part B treatment is encouraged to start within 7 weeks of the last dose of Part A study drug, although there is no limit to the interval so long as there is no intervening systemic treatment for the metastatic RCC.

Ipilimumab will be given 1 mg/kg every 3 weeks together with nivolumab 3 mg/kg every 3 weeks for up to 4 doses. **NOTE:** ipilimumab/nivolumab combination treatment must be completed by week 16 even if < 4 doses are administered. Nivolumab will revert to 360 mg every 3 weeks after the completion of combination treatment with ipilimumab for 4 doses (2 cycles) followed by nivolumab 480 mg IV every 4 weeks until toxicity, disease progression or a maximum of 60 total weeks (12 weeks induction, 48 weeks maintenance) beginning week 13 to 19 of Part B depending on how long it takes to recover from any side effects related to combination therapy. Patients may be dosed no less than 18 days from the previous dose of drug; and dosed up to 3 days after the scheduled date, if necessary.

Part B

Drug ¹	Dose	Route ⁴	Schedule ³	Cycle Length	Cycles/Weeks
Nivolumab	3 mg/kg	IV over 30 minutes	Day 1 and 22	6 weeks	C1 and C2 Weeks 1-12
Ipilimumab	1mg/kg	IV over 30 minutes			
Nivolumab	360 mg	IV over 30 minutes	Day 1 and 22	6 weeks	C3 and C4 Weeks 13-24
Nivolumab	480 mg	IV over 30 minutes	Day 1, 29 and 57	12 weeks	C5-C7 Weeks 25-60

¹ When study drugs (ipilimumab and nivolumab) are to be administered on the same day, separate infusion bags and filters must be used for each infusion. It is recommended that nivolumab be administered first. The second infusion will always be ipilimumab, and will start approximately 30 minutes after completion of the nivolumab infusion

² The dosing calculations should be based on the body weight where applicable. Institutional standards for recalculating the dose based on weight changes should be used. All doses should be rounded up or to the nearest milligram per institutional standard.

³ A window of \pm 3 days may be applied to all study visits to accommodate observed holidays, inclement weather, scheduling conflicts etc. Date and time of each drug administration should be clearly documented in subject's chart and electronic case report forms (eCRFs).

⁴ Infusion window of \pm 10 minutes

5.2 Concomitant Medications

5.2.1 Allowed Concomitant Medications

All treatments that the investigator considers necessary for a subject's welfare may be administered at the discretion of the investigator in keeping with the community standards of medical care.

5.2.2 Prohibited Concomitant Medications

Concomitant systemic or local anti-cancer medications or treatments are prohibited in this study while receiving ipilimumab/nivolumab treatments.

Patients may not use any of the following therapies during the study:

- Any non-study anti-cancer agent (investigational or non-investigational)
- Any other investigational agents
- Immunosuppressive agents (except as needed to treat toxicities that develop on therapy)
- Physiologic replacement doses of corticosteroids are permitted if required
- Any non-oncology vaccine therapies used for the prevention of infectious diseases (for up to 30 days prior to or after any dose of study drug)

NOTE: Patients are permitted to receive the seasonal influenza vaccine. If seasonal influenza vaccine is considered, killed vaccines are mandatory.

6. TOXICITIES AND DOSE DELAYS

The NCI Common Terminology Criteria for Adverse Events (CTCAE) v4.03 will be used to grade adverse events.

Subjects enrolled in this study will be evaluated clinically and with standard laboratory tests before and at regular intervals during their participation in this study as specified in Study Calendar & Evaluations.

Subjects will be evaluated for adverse events (all grades), serious adverse events, and adverse events requiring study drug interruption or discontinuation as specified in Study Calendar & Evaluations.

6.1 Dose Delays/Dose Modifications

There will be no dose modifications permitted. Dose reductions or dose escalations are not permitted.

6.1.1 Dose Delay Criteria

Dose delay criteria apply for all drug-related adverse events (regardless of whether or not the event is attributed to nivolumab, ipilimumab or both). Study drugs (both agents if on induction phase of Part B) must be held/omitted until treatment can resume. Please see Appendix A for AE management guidelines.

Nivolumab and ipilimumab administration should be omitted for the following:

- Any Grade ≥ 2 non-skin, drug-related adverse event, with the following exceptions:
 - Grade 2 drug-related fatigue or laboratory abnormalities that do not require a treatment delay (with the exception of Grade 3 AST, ALT or total bilirubin in patients with normal baseline values-see below).
- Any Grade 3 skin, drug-related adverse event
- Any Grade 3 drug-related laboratory abnormality, with the following exceptions:
 - Grade 3 amylase or lipase abnormalities that are not associated with symptoms or clinical manifestations of pancreatitis do not require a dose delay. It is recommended to consult with the principal investigator for Grade 3 amylase or lipase abnormalities.
 - If a subject has a baseline AST, ALT, or total bilirubin that is within normal limits, delay dosing for drug-related Grade ≥ 2 toxicity
 - If a subject has baseline AST, ALT, or total bilirubin within the Grade 1 toxicity range, delay dosing for drug-related Grade ≥ 3 toxicity
- Any adverse event, laboratory abnormality, or intercurrent illness which, in the judgment of the site investigator, warrants delaying the dose of study medication.

6.1.2 Criteria to Resume Treatment

Subjects may resume treatment with study drugs when the drug-related AE(s) resolve to Grade ≤ 1 or baseline value, with the following exceptions:

- Subjects may resume treatment in the presence of Grade 2 fatigue
- Subjects who have not experienced a Grade 3 drug-related skin AE may resume treatment in the presence of Grade 2 skin toxicity

- Subjects with baseline Grade 1 AST/ALT or total bilirubin who require dose delays for reasons other than a 2-grade shift in AST/ALT or total bilirubin may resume treatment in the presence of Grade 2 AST/ALT OR total bilirubin
- Subjects with combined Grade 2 AST/ALT AND total bilirubin values meeting discontinuation parameters (Section 6.3.3) should have treatment permanently discontinued
- Drug-related pulmonary toxicity, diarrhea, or colitis, must have resolved to baseline before treatment is resumed
- Drug-related endocrinopathies adequately controlled with only physiologic hormone replacement may resume treatment

If the criteria to resume treatment are met, the subject should restart treatment at the next scheduled timepoint per protocol (i.e., missed doses are NOT made up).

If treatment is delayed > 6 weeks, (from the first missed dose) the subject should be permanently discontinued from study therapy, except as specified in discontinuation section below.

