6.1.3 Discontinuation Criteria

Treatment should be permanently discontinued for the following:

- Any Grade 2 drug-related uveitis or eye pain or blurred vision that does not respond to topical therapy and does not improve to Grade 1 severity within the re-treatment period OR requires systemic treatment
- Any Grade 3 non-skin, drug-related adverse event lasting > 7 days, with the following exceptions for drug-related laboratory abnormalities, uveitis, pneumonitis, bronchospasm, diarrhea, colitis, neurologic adverse event, hypersensitivity reactions, and infusion reactions
 - Grade 3 drug-related uveitis, pneumonitis, bronchospasm, diarrhea, colitis, neurologic adverse event, hypersensitivity reaction, or infusion reaction of any duration requires discontinuation (**NOTE:** Subjects with Grade 3 diarrhea or colitis while on Part B ipilimumab/nivolumab combination therapy could resume nivolumab alone if toxicity resolves to at least Grade 1 off of immunosuppressive drugs by end of week 16. Nivolumab monotherapy cannot start until toxicity is resolved to at least Grade 1 off immunosuppression x 2 weeks and cannot begin before week 13 or after week 19.
- Grade 3 drug-related laboratory abnormalities do not require permanent treatment discontinuation except those noted below
 - Grade 3 drug-related thrombocytopenia > 7 days or associated with bleeding
 - Any drug-related liver function test (LFT) abnormality that meets the following criteria require discontinuation:
 - AST or ALT > 8 x ULN
 - Total bilirubin > 5 x ULN
 - Concurrent AST or ALT > 3 x ULN and total bilirubin > 2 x ULN

- Any Grade 4 drug-related adverse event or laboratory abnormality, except for the following events which do not require discontinuation:
 - Isolated Grade 4 amylase or lipase abnormalities that are not associated with symptoms or clinical manifestations of pancreatitis and:
 - Decrease to < Grade 4 within 2 weeks of onset in the absence of immunosuppressive therapy.
 - Decrease to < Grade 4 and maintain < Grade 4 for a minimum of 1 week after stopping immunosuppressive therapy.
 - Isolated Grade 4 electrolyte imbalances/abnormalities that are not associated with clinical sequelae and are corrected with supplementation/appropriate management within 72 hours of their onset
- Any dosing interruption lasting > 6 weeks (from scheduled dose) with the following exceptions:

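### Sections 6.1.2 and 6.1.3 set different resolution levels for restarting nivolumab after Grade 3 diarrhea or colitis in Part B, and neither says which governs

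*Combined protocol and SAP*

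**What the plan says.** Section 6.1.2 opens with a general rule: "Subjects may resume treatment with study drugs when the drug-related AE(s) resolve to Grade ≤ 1 or baseline value, with the following exceptions". One of the listed exceptions is specific to pulmonary and bowel toxicity: "Drug-related pulmonary toxicity, diarrhea, or colitis, must have resolved to baseline before treatment is resumed". It names no grade, no study part and no drug.

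Section 6.1.3 lists Grade 3 diarrhea and colitis among the events for which a reaction "infusion reaction of any duration requires discontinuation". A NOTE then makes one carve-out. A patient with Grade 3 diarrhea or colitis on the Part B combination "could resume nivolumab alone if toxicity resolves to at least Grade 1 off of immunosuppressive drugs by end of week 16". The NOTE adds: "Nivolumab monotherapy cannot start until toxicity is resolved to at least Grade 1 off immunosuppression x 2 weeks and cannot begin before week 13". The latest permitted start is week 19.

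On interruptions, 6.1.2 says: "If treatment is delayed > 6 weeks, (from the first missed dose) the subject should be permanently discontinued from study therapy". That sentence ends by deferring to the discontinuation section. Section 6.1.3 repeats the six-week limit and lists two exceptions: prolonged steroid tapers and non-drug-related reasons. Section 6.3 repeats the limit again and sends any exception to the study chair for approval.

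**The concern.** For drug-related diarrhea and colitis, 6.1.2 tightens the general rule to baseline. The NOTE in 6.1.3, for the same toxicities, accepts Grade 1. Whether a given patient is re-dosed can then depend on which section the site reads. The timing rules raise a similar question: the NOTE imposes a wait that can exceed the six-week limit, and the text does not say that the NOTE is an exception to that limit.

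At stake is a safety rule in Part B, which expects roughly 60 clear cell and 20 non-clear cell patients and has its own safety analysis (section 12.9). Two sites could handle the same patient differently, and both could cite the protocol.

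**Working it through.** The plan gives no figure to reproduce here. The check is a comparison of the text and a count of days.

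**1. Which rule applies to which event**

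- Grade 2 diarrhea or colitis: 6.1.1 holds the drugs for "Any Grade ≥ 2 non-skin, drug-related adverse event, with the following exceptions". Restart falls under the 6.1.2 bullet, so the level is baseline. Section 6.1.2 states no period off immunosuppression.
- Grade 3 in Part A: permanent discontinuation under 6.1.3, with no carve-out.
- Grade 3 on the Part B combination: discontinuation by default, with the NOTE permitting nivolumab alone at Grade 1 or better, after 2 weeks off immunosuppression, within weeks 13 to 19.

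**2. Where the two resolution levels disagree** (Grade 3 event in Part B, all other NOTE conditions met)

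| Baseline grade | Residual grade | 6.1.2 bullet | 6.1.3 NOTE |
|---|---|---|---|
| 0 | 0 | met | met |
| 1 | 1 | met | met |
| 0 | 1 | not met | met |

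The conflict lies in the last row.

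**3. Whether any text settles it**

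- The deferral from 6.1.2 to the discontinuation section is attached to the six-week sentence, not to the diarrhea and colitis bullet.
- The NOTE does not mention the baseline requirement.
- The Part B treatment plan (section 5.2) starts maintenance nivolumab in weeks 13 to 19 according to recovery, but gives no resolution grade.
- The gastrointestinal algorithm in Appendix A is a figure not shown in the available text, so it cannot be checked.

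**4. Timing**

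Inputs: section 5.2 (Part B) gives combination doses on days 1 and 22 of two 6-week cycles. Counted from the start of Part B, these are days 1, 22, 42 + 1 = 43 and 42 + 22 = 64. Week 13 begins on day 12 × 7 + 1 = 85. The interruption limit is 6 × 7 = 42 days.

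Shortest wait = 85 − day of first missed dose.

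- Dose 2: 85 − 22 = 63 days, which is 63 − 42 = 21 days over the limit.
- Dose 3: 85 − 43 = 42 days, exactly at the limit; any later restart exceeds it.
- Dose 4: 85 − 64 = 21 days, within the limit. The limit is reached on day 64 + 42 = 106, the first day of week 16 (15 × 7 + 1). Restarts after that, up to the end of week 19 (day 19 × 7 = 133), exceed it.

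These are nominal days. The ±3-day visit window could move the dose 3 case to either side of the limit, but not the dose 2 case.

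**5. Whether the six-week exceptions cover this wait**

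A patient still on a prolonged steroid taper has an exception under 6.1.3. A patient who recovers early and waits only because nivolumab "cannot begin before week 13 or after week 19" is not clearly covered by either listed exception: the wait comes from the NOTE itself, after a drug-related event. Section 6.3 would still require the study chair's approval.

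**The case against.** The strongest reply is that the NOTE is a deliberate, specific exception. It names the grade, the study part, the regimen and the drug, and it governs a patient who has already met a discontinuation criterion. The 6.1.2 bullet is a general rule for restarting held drugs. The week 13 to 19 start in section 5.2 fits that reading. It may well be what was intended, but the text does not say so. The 6.1.2 bullet is itself the specific rule for diarrhea and colitis, and the NOTE is worded as relief from discontinuation, not from the baseline requirement.

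A reader might infer that the worse event has the looser rule overall. The documents do not support that. Discontinuation is the default for Grade 3, ipilimumab is not resumed, 2 weeks off immunosuppression are required, and restart is confined to a window. A Grade 2 event under 6.1.2 faces none of these conditions. Only the resolution grade is looser.

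A reader might also infer that the six-week rule necessarily ends treatment for patients the NOTE would readmit. That goes too far. The 6.1.2 sentence defers to the discontinuation section, which contains both the NOTE and the steroid-taper exception, and 6.3 allows approved exceptions. What stands is that the NOTE is not named among the interruption exceptions.

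Finally, the 34% in section 1.5 might be taken as the share affected. It covers all Grade 3 or 4 treatment-related events on this schedule in the cited phase I trial. Section 10.2.7 gives drug-related diarrhea in 28.6% on the schedule and says most of the listed events were Grade 1-2. Neither figure is a rate of Grade 3 diarrhea or colitis.

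**Conclusion.** The two sections conflict on one element. After Grade 3 diarrhea or colitis on the Part B combination, a patient with baseline Grade 0 and residual Grade 1 can qualify for nivolumab alone under the 6.1.3 NOTE and does not qualify under the 6.1.2 bullet. No available text says which governs.

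The secondary timing gap is real but smaller. Nominal waits are at least 63 days when dose 2 is the first missed and at least 42 days when dose 3 is, against a 42-day limit whose listed exceptions omit the NOTE.

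How many patients this touches cannot be stated from the documents, and an effect on Part B results is possible but not shown. The conclusion assumes that the Appendix A gastrointestinal figure does not settle the question; if it does, the remaining defect is a missing cross-reference. Because the text decides whether a patient is re-dosed, it should be corrected even though the affected group may be small.

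**What to change.** Reconcile the 6.1.2 bullet, the 6.1.3 NOTE and the six-week rule in 6.1.2, 6.1.3 and 6.3. The amended text should:

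- state one governing resolution criterion for restart after Grade 3 diarrhea or colitis in Part B, and cross-refer 6.1.2 and the NOTE to each other;
- state whether the NOTE is an exception to the six-week rule and, if so, whether study chair approval under 6.3 is still needed;
- agree with the gastrointestinal algorithm in Appendix A, which should be checked for consistency.

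The choice of criterion belongs to the clinical team; this point takes no view on it. The cost is wording in an amendment, and a clarification memo to sites can go out first.

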6.1.3 Discontinuation Criteria

Treatment should be permanently discontinued for the following:

- Any Grade 2 drug-related uveitis or eye pain or blurred vision that does not respond to topical therapy and does not improve to Grade 1 severity within the re-treatment period OR requires systemic treatment
- Any Grade 3 non-skin, drug-related adverse event lasting > 7 days, with the following exceptions for drug-related laboratory abnormalities, uveitis, pneumonitis, bronchospasm, diarrhea, colitis, neurologic adverse event, hypersensitivity reactions, and infusion reactions
 - Grade 3 drug-related uveitis, pneumonitis, bronchospasm, diarrhea, colitis, neurologic adverse event, hypersensitivity reaction, or infusion reaction of any duration requires discontinuation (**NOTE:** Subjects with Grade 3 diarrhea or colitis while on Part B ipilimumab/nivolumab combination therapy could resume nivolumab alone if toxicity resolves to at least Grade 1 off of immunosuppressive drugs by end of week 16. Nivolumab monotherapy cannot start until toxicity is resolved to at least Grade 1 off immunosuppression x 2 weeks and cannot begin before week 13 or after week 19.
- Grade 3 drug-related laboratory abnormalities do not require permanent treatment discontinuation except those noted below
 - Grade 3 drug-related thrombocytopenia > 7 days or associated with bleeding
 - Any drug-related liver function test (LFT) abnormality that meets the following criteria require discontinuation:
 - AST or ALT > 8 x ULN
 - Total bilirubin > 5 x ULN
 - Concurrent AST or ALT > 3 x ULN and total bilirubin > 2 x ULN

- Any Grade 4 drug-related adverse event or laboratory abnormality, except for the following events which do not require discontinuation:
 - Isolated Grade 4 amylase or lipase abnormalities that are not associated with symptoms or clinical manifestations of pancreatitis and:
 - Decrease to < Grade 4 within 2 weeks of onset in the absence of immunosuppressive therapy.
 - Decrease to < Grade 4 and maintain < Grade 4 for a minimum of 1 week after stopping immunosuppressive therapy.
 - Isolated Grade 4 electrolyte imbalances/abnormalities that are not associated with clinical sequelae and are corrected with supplementation/appropriate management within 72 hours of their onset
- Any dosing interruption lasting > 6 weeks (from scheduled dose) with the following exceptions:
 - Dosing interruptions to allow for prolonged steroid tapers to manage drug-related adverse events are allowed. Prior to re-initiating treatment in a subject with a dosing interruption lasting > 6 weeks, the sponsor-investigator must be consulted. Tumor assessments should continue as per protocol even if dosing is interrupted
 - Dosing interruptions > 6 weeks that occur for non-drug-related reasons may be allowed if approved by the sponsor-investigator. **Prior to re-initiating treatment in a subject with a dosing interruption lasting > 6 weeks, the Principal Investigator must be consulted.** Tumor assessments should continue as per protocol even if dosing is interrupted.
- Any adverse event, laboratory abnormality, or intercurrent illness which, in the judgment of the site investigator, presents a substantial clinical risk to the subject with continued nivolumab or ipilimumab dosing

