3.3 Inclusion/Exclusion Criteria- Part B

1. Must meet eligibility criteria for initiation of Part A with the exception of being allowed to have prior nivolumab in Part A of this protocol.
2. Must have evidence of either RECIST 1.1 defined Disease Progression or Stable Disease 1 year after initiating nivolumab therapy
3. Tumor biopsy prior to combination treatment is mandatory. If a biopsy/resection of a new lesion or primary tumor and slow freezing of fresh tissue for single cell RNAseq study (as specified in the CLM) is not feasible, the subject is not eligible for the study. All biopsies must be core needle or excisional. Fine needle aspirate is not acceptable.
4. Must not have had a Grade ≥ 3 irAE on nivolumab monotherapy (excluding endocrine toxicity managed with replacement therapy).
5. Must not have untreated brain metastases.
6. Must not have had major surgery or radiation therapy within 14 days of starting study treatment.
7. Must not have active autoimmune disease (see protocol for exceptions).
8. Must not have a concurrent medical condition requiring use of systemic corticosteroids with prednisone >10 mg per day.
9. Must not have had prior systemic therapy for Stage IV RCC (except for nivolumab as part of part A of this protocol).

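### For a hormone-controlled endocrinopathy that was a clinical Grade 3 event lasting over 7 days, or Grade 4, Section 6.1.2 permits resumption and Section 6.1.3 directs permanent discontinuation, with no stated precedence

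*Combined protocol and SAP*

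**What the plan says.** Section 6.1.2 sets the general condition for restarting after a hold: "Subjects may resume treatment with study drugs when the drug-related AE(s) resolve to Grade ≤ 1 or baseline value, with the following exceptions". One of those exceptions is endocrine: "Drug-related endocrinopathies adequately controlled with only physiologic hormone replacement may resume treatment". It carries no grade ceiling, no duration limit and no reference to the discontinuation section.

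Section 6.1.3 opens with "Treatment should be permanently discontinued for the following". Two of its entries matter here.

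- Grade 3: "Any Grade 3 non-skin, drug-related adverse event lasting > 7 days, with the following exceptions for drug-related laboratory abnormalities", and the list of exceptions continues with "uveitis, pneumonitis, bronchospasm, diarrhea, colitis, neurologic adverse event, hypersensitivity reactions, and infusion reactions". Grade 3 laboratory abnormalities are then released from discontinuation, apart from specified platelet and liver-test cases.
- Grade 4: "Any Grade 4 drug-related adverse event or laboratory abnormality, except for the following events which do not require discontinuation". The events listed are certain isolated amylase or lipase abnormalities and certain isolated electrolyte abnormalities.

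Neither list names endocrinopathy, and nothing in the rest of 6.1.3 adds it.

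On entry to Part B, Section 3.3 item 4 reads: "Must not have had a Grade ≥ 3 irAE on nivolumab monotherapy (excluding endocrine toxicity managed with replacement therapy". Section 5.2 (Part B) also exempts endocrine toxicity, but from an exclusion worded as Grade 3 only. The opening text of Section 5 repeats the Grade 3 exclusion for Part B without any endocrine exemption.

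**The concern.** These are working instructions on whether a patient stays on study drug, in a multicenter trial. A site that reads 6.1.2 may restart a patient whose endocrinopathy is controlled. A site that reads 6.1.3 will stop the same patient for good. Both can say they followed the protocol.

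Toxicity of nivolumab monotherapy is a secondary objective. If the rule is applied differently by site, the count of patients who stopped for toxicity partly reflects which section each site used. The same ambiguity invites disputes over what counts as a protocol deviation.

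**Working it through.** The plan gives no figure to reproduce; the check is a comparison of the rules.

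**Step 1. Cases for a drug-related endocrinopathy controlled on physiologic replacement**

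| Event | 6.1.2 | 6.1.3 | Opposed? |
|---|---|---|---|
| Grade 2 | resumption permitted | no stop | no |
| Grade 3 clinical, 7 days or less | resumption permitted | no stop | no |
| Grade 3, laboratory-only | resumption permitted | laboratory exception, no stop | no |
| Grade 3 clinical, more than 7 days | resumption permitted | permanent stop | **yes** |
| Grade 4, outside the enzyme and electrolyte exceptions | resumption permitted | permanent stop | **yes** |

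**Step 2. Does the text say which section prevails?** No general precedence statement appears. Where 6.1.2 means to give way, it says so: "Subjects with combined Grade 2 AST/ALT AND total bilirubin values meeting discontinuation parameters (Section 6.3.3) should have treatment permanently discontinued". Its paragraph on delays beyond 6 weeks also defers to the discontinuation section. Where 6.1.2 means to limit by grade, it says that too, for fatigue, skin and liver tests. The endocrine bullet does neither. The liver bullet's own cross-reference is to a Section 6.3.3 that does not appear in the protocol; the liver criteria stand in 6.1.3.

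**Step 3. Suppose 6.1.3 prevails.** A Part A patient with a qualifying event stops nivolumab permanently. Section 3.3 item 4 does not bar that patient from Part B if the event is managed with replacement, and Section 5.2 sets no limit on the interval before Part B provided there is no intervening systemic therapy for metastatic disease. At progression the patient could, if otherwise eligible, receive nivolumab again, with ipilimumab. The clash is clearest for Grade 4. Item 4 covers Grade 3 and above, whereas 6.1.3 stops Grade 4 whatever its duration. For Grade 3, item 4 could be satisfied by short or laboratory-only events alone, but it is not written that way. Section 5 read alone gives a third answer, because it omits the endocrine exemption.

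**Step 4. Size.** The documents give no rate of Grade 3 or 4 endocrine events, and no split by duration or by laboratory-only status. Section 1.4 reports Grade 3 or 4 toxicity of all kinds in 14% and 19% of nivolumab patients in two earlier trials. Assuming those rates carried over to the 134 + 40 = 174 planned Part A patients, events of every type would number 174 × 0.14 ≈ 24 to 174 × 0.19 ≈ 33 patients. The conflict concerns only the endocrine part of these, and within it only Grade 4 or prolonged clinical Grade 3 events that are controlled on replacement. This is an outer limit under that assumption, not an estimate. Events on the Part B combination would add to it.

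**The case against.** The strongest reply is that the sections work in sequence. Section 6.1.1 holds drug, 6.1.2 says when a held patient may restart, and 6.1.3 removes some patients from that path altogether. A permissive rule does not compel anything, so a directive to stop takes over. The general resume rule and the pulmonary and bowel bullet in 6.1.2 are also ungraded, yet nobody would read them as cancelling 6.1.3. On this view the endocrine bullet still has work to do: Grade 2 events, short Grade 3 events and laboratory-only Grade 3 abnormalities.

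Much of this stands. A reader might infer that the protocol requires the same patient to be both restarted and stopped. It does not: one section permits what another forbids, and the sequential reading is available. But the protocol does not state that reading, and it leads to the Part B difficulty in step 3. Section 12.6 treats Part B as a separate study with baseline reset, which may explain that difficulty, but 6.1.3 does not confine its permanent stop to one Part.

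Two further limits stand. Section 6.1.1 refers to Appendix A, whose endocrinopathy algorithm is a figure not reproduced in the text available. It may guide sites, although the written sections would still differ.

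A reader might also infer a distorted 1-year PFS estimate. The documents do not support that. Section 12.10 assesses PFS in all registered clear cell subjects, Section 6.3 keeps patients who stop therapy in follow-up, and the imaging footnote to the study calendar provides for recording later tumor evaluations. Nor can an assumed 1% to 5% of 174 (about 2 to 9 patients) be taken as the number in conflict: that range has no source in the documents and would include short and laboratory-only events.

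**Conclusion.** The point holds in narrow form. For hormone-controlled, drug-related endocrinopathy that was a clinical Grade 3 event lasting more than 7 days or a Grade 4 event, 6.1.2 and 6.1.3 point opposite ways and precedence is unstated. Giving precedence to 6.1.3 moves the inconsistency to 3.3 item 4 and 5.2 rather than removing it.

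The number of patients cannot be derived and is probably small. What is at stake is consistent treatment decisions and comparable toxicity-discontinuation counts across sites. The conclusion rests on the written sections alone, since the Appendix A algorithm could not be read. It is worth correcting because the rule governs stopping treatment and the correction is small.

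**What to change.** In one amendment, reconcile Sections 6.1.2, 6.1.3, 3.3 item 4, 5.2 (Part B) and the Part B paragraph of Section 5, so that one rule for endocrinopathy applies by grade and duration. State whether 6.1.2 or 6.1.3 takes precedence, and whether a permanent stop in Part A bears on entry to Part B. Check the result against the Appendix A endocrinopathy algorithm, and correct the reference to Section 6.3.3 at the same time.

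Which patients should stop or continue is a clinical decision for the sponsor-investigator; the request is only that the sections agree.

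The cost is a few lines of text, with no added visits, data or sample size. If patients have already met this situation, listing how each was handled would make the discontinuation counts interpretable.
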